#### **4.3 Justification for Dose**

The dose is based on the approved United States label (United States Prescribing Information).

Prophylactic treatment regimens should be guided by clinical judgment based on individual patient characteristics and treatment response.

#### **4.4 End of Study Definition**

A participant is considered to have completed the study if he/she has completed all phases of the study including the last visit or the last scheduled procedure shown in the SoA. The end of study (EOS) is defined as the date of the clean database.

#### **Primary completion**

The primary completion is defined as the date when all participants have completed the last visit for the primary endpoint (i.e. measurement of favorable outcomes based on changes in ABR and frequency of administration).

### **5. Study Population**

Previously-treated adolescent/adult ( $\geq 12$  years) patients with congenital hemophilia A on continuous prophylaxis with an SHL FVIII product for at least 6 consecutive months within the previous 12 months prior to the screening visit will be included. Medical records or a detailed participant documentation (i.e. diary, etc.) covering the last year is required to confirm the participant's prophylaxis treatment modality.

#### **5.1 Inclusion Criteria**

Participants are eligible to be included in the study only if all of the following criteria apply:

##### **Age**

1. Participants must be  $\geq 12$  years of age inclusive, at the time of signing the informed consent/assent.

##### **Types of Participants and Disease Characteristics**

2. Previously-treated patients ( $\geq 150$  EDs) with congenital hemophilia A.

3. Prophylaxis with any SHL FVIII product with a stable frequency for at least 6 consecutive months within the last 12 months prior to screening, before entering the study and documented in medical records.
  - Stable frequency is defined as a minimum of 18 weeks of treatment in a 6 (consecutive) calendar month period in the 12 months prior to screening.
  - Patients can be on any non-Jivi EHL between the 6 -month stable SHL prophylaxis period and start of study treatment.
4. Documented bleeding rate (ABR) while on stable frequency prophylaxis for at least 6 consecutive months within the last 12 months prior to screening.
5. No current evidence ( $\geq 0.6$  BU/mL) of FVIII inhibitors.
  - If a participant has had a positive inhibitor titer in the past ( $\geq 0.6$  BU/mL on 2 occasions) but has been tolerized for at least 1 year since the last positive titer with at least 1 negative inhibitor assay test during that period, they can be enrolled.
  - If a participant has had a positive inhibitor titer in the past ( $\geq 0.6$  BU/mL) but did not require tolerization and has had at least 1 negative inhibitor assay test during a minimum period of at least 1 year since the last positive titer, they can be enrolled.
6. If they are human immunodeficiency virus (HIV) positive, cluster of differentiation 4 (CD4)+ lymphocyte count should be  $> 200/\text{mm}^3$  within 1 year before entering the study and documented in medical records.
7. Participants who are willing to complete an electronic diary (eDiary).

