**Amendment 3 (02 OCT 2023)****Overall Rationale for the Amendment:**

It was planned to enroll a maximum of 70 participants such that approximately 60 evaluable participants would complete the study. Due to the observed rate of recruitment, it will not be feasible to enroll 70 participants within the planned recruitment period. Given the actual recruitment (as of August 2023), it is assumed that only 20-25 participants will be enrolled by the end of 2023. The protocol was updated to describe the anticipated reduced sample size and the impact on the precision of estimates.

Furthermore, the inclusion criteria were adjusted to reduce restrictions to enrollment.

Although the change in inclusion criteria has the potential to introduce bias in comparisons to patients enrolled prior to the amendment, the risk is thought to be minimal given the 2 possible extreme scenarios below:

- o 1 – interruptions in treatment (eg, insurance, migration): a maximum period of 6 months (assuming untreated during that time) is not expected to dramatically change patients' disease phenotype such that it would reflect during Jivi prophylaxis while on study
- o 2 – patients treated with an extended half-life (EHL) prior to study entry: the reason for switching to an EHL following stable SHL prophylaxis could be due to external conditions unrelated to patients' bleeding phenotype (eg, formulary changes, insurance requirements, patient preference, etc.). Nevertheless, if the change to an EHL treatment was due to a patient's bleeding phenotype and/or any structural differences compared to any patients enrolled before amendment 3, the risk of bias is thought to be low, since any data from the time of EHL treatment are excluded from the risk score calculation for those patients remaining to be enrolled.

Due to the decision to no longer pursue enrolling participants from Colombia, the protocol is amended back to a single country United States study.

The changes incorporated in this amendment are described in the table below. Edits to update amendment number and dates in the current version, and minor editorial changes for style have been made, but are not documented in the table.

Section # and Name	Description of Change	Brief Rationale

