### **6.3 Measures to Minimize Bias: Randomization and Blinding**

This is an open-label, single treatment arm study, and no randomization or masking will be performed. All participants will receive study intervention and will be allocated to a prophylaxis regimen based on the total risk score determined at baseline. The retrospective data collection on bleed frequency before trial for comparison may be biased towards lower bleed rates due to incomplete documentation and collection from any given 6-month period within 12 months of study screening, as it is assumed that the time a subject is not on stable prophylaxis (up to 6 months prior to enrollment) does not have an influence on the occurrence of bleeds during the study period. This would affect the outcome negatively, because the data collection during the study is prospective. Nevertheless, the pre-study bleed rate has been documented in all clinical studies based on participant diaries as per local standard of care and has been seen to provide a good estimate of the participant's bleed rate.

Participants will be identified by a unique participant number with 9 digits once the ICFs (and assent forms) are signed. The first 5 digits will identify the country and study site; the last 4 digits are assigned to the participant of the specific site in increasing order.

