### 9.4.2 Primary Endpoint

The analysis of the primary endpoint will be performed on the mITT population. The entire study treatment period will be analyzed regardless of the dosing regimen.

The proportion and 95% CI of participants with favorable outcome on the risk score-selected prophylaxis regimen will be described. The proportion will be provided overall, as well as by assigned prophylaxis regimen.

Favorable outcome is defined as no change of the score-assigned dosing regimen with one of the following intra-individual measures:

- improved ABR and decreased frequency of administration.
- improved ABR with similar frequency of administration.
- decreased frequency of administration and similar ABR.

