#### Definitions

- No regimen change during study: participant is treated according to the score-assigned regimen and does not deviate or switch frequency.
- Improved ABR: Reduction from pre-study ABR is  $\geq 1$ .
- Similar ABR: Absolute change from pre-study ABR is  $< 1$ .

- Worse ABR: Increase from pre-study ABR is  $\geq 1$ .
- Decreased frequency of administration: Reduction from pre-study in number of infusions per month is  $\geq 2$ .
- Similar frequency of administration: Absolute change from pre-study in number of infusions per month  $< 2$ .
- Worse frequency of administration: Increase from pre-study in number of infusions per month is  $\geq 2$ .

Pre-study ABR and treatment frequency is based on data from a minimum of 6 continuous months (up to a maximum of 12 months) of stable SHL prophylaxis at any given time within the 12 months prior to screening. Stable SHL prophylaxis is defined as a minimum of 18 weeks of treatment in a 6 (consecutive) calendar month period in the 12 months prior to the screening visit.

A switch to a higher frequency regimen due to a bleed during study is considered as non-favorable outcome, whereas participants who switch due to other reasons (e.g. personal decision, study compliance issues, or changes in physical activity level) will be censored at time of switch.

The number (frequency) of participants switching the risk score-selected dosing regimen will be summarized.

As sensitivity analyses, the proportion of participants with favorable outcome on the risk score-selected prophylaxis regimen will be presented by inhibitor history.

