#### **4.2.3 Sensitivity Analysis**

The following analysis will be performed if numbers of participants in the mITT population with and without history of FVIII inhibitors are each  $\geq 5$ : As sensitivity analyses, the proportion of participants with favorable outcome on the risk score-selected prophylaxis regimen will be presented by inhibitor history.

The following analysis will be performed if  $> 3$  participants in the safety analysis set are excluded from the mITT: The proportion of participants with favorable outcome will be reported for the safety analysis set, assigning non-favorable outcome to participants who discontinued or switched regimen prior to 4 months.

A further sensitivity will be conducted, assigning non-favorable outcome to all participants who discontinued or switched regimen at any time during study.

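### Gains already made on another EHL before Day 1 can count toward favorable outcome, and no planned analysis separates those participants

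*Protocol*

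**What the plan says.** Criterion 3 in Protocol 5.1 requires at least 6 consecutive months of SHL prophylaxis at a stable frequency in the 12 months before screening. It then adds a clause beginning "Patients can be on any non-Jivi EHL between the", which allows another EHL from the end of that SHL period until Jivi starts. The SoA provides for this with a separate wash-out for those whose previous product was an EHL.

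The comparator was left where it was. Under Protocol 9.4.2, pre-study ABR and frequency rest on "stable SHL prophylaxis at any given time within the 12 months prior to screening", and SAP 4.1.1.1 and 4.1.1.4 take both from the stable SHL period. Frequency counts as decreased when "Reduction from pre-study in number of infusions per month is" at least 2. For a participant who stays on the assigned regimen, one of the three routes to a favorable outcome is "decreased frequency of administration and similar ABR".

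The protocol discusses the bias in three places:

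- The Amendment 3 rationale accepts that "the change in inclusion criteria has the potential to introduce bias in comparisons to patients enrolled prior to the amendment" but rates the risk as minimal. For EHL users the reason is that EHL-period data do not enter the risk score.
- Section 4.1 says that SHL versus score-based Jivi is the comparison intended, and that bringing in another period would bias it.
- Section 6.3, writing about bleeds during the study, says "it is assumed that the time a subject is not on stable prophylaxis (up to 6 months prior to enrollment) does not have an influence".

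SAP 4.2.3 plans sensitivity analyses by inhibitor history, on the safety analysis set, and by "assigning non-favorable outcome to all participants who discontinued or switched regimen at any time during study". The last of these concerns regimen changes on Jivi, not the product used before Visit 2.

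**The concern.** The primary objective is the effect of the score when a participant switches from an SHL product to Jivi. Someone who has already moved to another EHL made that change earlier, without the score. If infusions or bleeds fell at that point, the comparison with the older SHL period places the fall inside the study result.

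The reasons given do not reach this. Leaving EHL data out of the score protects the score's inputs. Declaring SHL versus Jivi as the intended comparison justifies the baseline, but does not show that a reduction made on a third product came from the score-selected regimen. The assumption in Section 6.3 is about bleeds and says nothing on infusion frequency. At stake is how to read a single proportion from 20-25 people, where a few participants matter.

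**Working it through.** **Inputs.** Formula from SAP 4.1.1.4: frequency = 30.4375 × prescribed doses / days, rounded to 2 decimals. Thresholds: a change of -2 or lower is decreased, between -2 and 2 similar, 2 or higher worse. EHL intervals of 3 to 5 days come from Protocol 2.1. SHL 3x/week is an assumption (the middle category of Table 4-1). The low-risk regimen is taken as Q7D.

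**Reproducing the SAP's figures.** High risk: 30.4375 × 52/182 = 8.6964. Low risk: 8 + 6 + 18 = 32 doses, and 30.4375 × 32/182 = 5.3516. Both match. The SAP gives no medium-risk figure. The same rule gives 8 + 31 = 39 doses, and 30.4375 × 39/182 = 6.52.

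**Example.** SHL 3x/week: 30.4375 × 3/7 = 13.04. EHL 2x/week: 30.4375 × 2/7 = 8.70. Jivi 2x/week: 8.70. Against SHL the change is -4.35 (-4.34 after the SAP's rounding), so decreased. Against the product replaced it is 0.00, so similar. With a similar ABR the participant is favorable on the first comparison and not on the second.

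**All combinations.**

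| Comparator (infusions/month) | Jivi 2x/week (8.70) | Jivi Q5D (6.52) | Jivi Q7D (5.35) |
|---|---|---|---|
| SHL 3x/week (13.04) | -4.34 decreased | -6.52 decreased | -7.69 decreased |
| EHL every 3 days (10.15) | -1.45 similar | -3.63 decreased | -4.80 decreased |
| EHL 2x/week (8.70) | 0.00 similar | -2.18 decreased | -3.35 decreased |
| EHL every 4 days (7.61) | +1.09 similar | -1.09 similar | -2.26 decreased |
| EHL every 5 days (6.09) | +2.61 worse | +0.43 similar | -0.74 similar |

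Of the 12 EHL cells, 7 lose the decreased label and 5 keep it. With SHL 2x/week (8.70), the Jivi 2x/week regimen is already similar against SHL (0.00), so no frequency credit arises there.

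**Effect on the primary proportion.** One reclassified participant is 1/20 = 5 points or 1/25 = 4 points. The number is not in the documents, so a range of assumed flips is shown, with Clopper-Pearson intervals:

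| Flips | N = 20 | N = 25 |
|---|---|---|
| 0 | 14/20 = 70% [45.7; 88.1] | 17/25 = 68% [46.5; 85.1] |
| 1 | 13/20 = 65% [40.8; 84.6] | 16/25 = 64% [42.5; 82.0] |
| 2 | 12/20 = 60% [36.1; 80.9] | 15/25 = 60% [38.7; 78.9] |
| 5 | 9/20 = 45% [23.1; 68.5] | 12/25 = 48% [27.8; 68.7] |

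The zero-flip rows match Protocol Table 9-1. Excluding participants moves the result less than reclassifying them: leaving out two favorable participants at N = 20 gives 12/18 = 66.7% [41.0; 86.7].

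**Treatment gap.** Here the sequence is 13.04, then none, then Jivi. The last prophylaxis is still SHL, so the change to the Jivi frequency happens at Day 1 and no earlier reduction is credited. What remains is a baseline that does not adjoin the study period and rests on the untested assumption in Section 6.3.

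**The case against.** The best reply is that the baseline is a stated and defended choice. Section 4.1 names SHL versus score-based Jivi as the target, and a participant going straight from SHL 3x/week to Jivi 2x/week also scores -4.35, so the EHL in between does not alter the planned classification. A favorable outcome further requires staying on the assigned regimen and no worsening of ABR, both observed on Jivi. This stands, and is why the primary analysis should not change. It does not answer whether a pre-entry gain is due to the score.

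The example is also a case that suits the point. The 2x/week regimen needs a score above 4. With ABR of 1 or less (-2), the other four items add at most 1 + 2 + 2 + 1 = 6, for a total of 4. Every high-risk participant therefore had an SHL ABR above 1, and some could qualify through improved ABR with similar frequency. That also stands: not every lost decreased label costs a favorable outcome.

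SAP 4.6.2 already tabulates the dates of the SHL period and the most recently discontinued treatment, and participant data will be listed. These help to identify the participants, but they do not recompute the primary proportion.

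Finally, the study is descriptive, and the protocol concedes a CI width of 42.4 points for 14/20. That limits the weight of the point.

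**Conclusion.** The point holds in a limited form. For participants who moved from SHL to another EHL before the study, a frequency or ABR gain reached before Day 1 can be counted as favorable on the score-selected regimen, and no planned analysis shows how much of the result this is. The size is 4 to 5 points for each participant whose favorable status flips. The frequency calculation assumes SHL 3x/week, EHL intervals of 3 to 5 days and, for the low-risk regimen, Q7D. The ABR route is not quantified. The number affected is unknown, limited to those enrolled after Amendment 3, and possibly zero.

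A reader might infer three stronger claims, none of which the documents support:

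- That every EHL user inflates the result. Five of the 12 combinations stay decreased against the EHL, and SHL 2x/week followed by Jivi 2x/week earns no frequency credit.
- That gap participants also bring in an earlier reduction. They made none on prophylaxis, and their issue is the non-adjacent baseline.
- That the protocol overlooks the choice of comparator. Section 4.1 states and defends it.

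**What to change.** Keep the SHL comparison as the primary analysis. Add to SAP 4.2.3:

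- the number of participants with non-Jivi EHL use between the stable SHL period and Visit 2 and, separately, the number with a treatment gap in that interval, with a stated rule for how long an untreated interval must be to count;
- the primary proportion with its Clopper-Pearson CI, excluding these participants.

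No new data should be needed. Protocol 8.1.3 records all FVIII products within 12 months, and SAP 4.6.2 already uses the SHL period dates and the last treatment with its dosing frequency. If both counts are zero, one sentence in the report closes the matter.

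The cost is one more table with fewer participants and a wider interval. If five of 20 were excluded, Table 9-1 gives CI widths of 38.8 to 51.4 points at N = 15, against 30.5 to 43.8 at N = 20.

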### Sex and Contraceptive/Barrier Requirements

8. Male or female participants

Contraceptive use should be consistent with local regulations regarding the methods of contraception for those participating in clinical studies.

- Male participants: It has been shown that there is no target-related specific transport mechanism for Jivi into semen or from semen into the conceptus. Following administration to a male participant, Jivi would not be bioavailable via seminal delivery to the developing conceptus of an untreated partner. Therefore, no method of contraception for male participants is needed.
- Female participants of childbearing potential (see [Section 11.6](#)) can only be included in the study if a pregnancy test is negative at the screening visit and if they agree to use adequate contraception during the study and until 8 weeks (inclusive) after last dose of study intervention. Adequate contraception is defined as any combination of at least 2 effective methods of birth control, of which at least 1 is a physical barrier (e.g. condoms with hormonal contraception or implants or combined oral contraceptives, certain intrauterine devices).
  - For adolescent (nulliparous) participants, long-acting reversible contraception (LARC) methods are considered first-line options.
- Postmenopausal females (no menses for 12 months without an alternative medical cause; see [Section 11.6](#)) are not required to use contraception. A high follicle-

stimulating hormone (FSH) level in the postmenopausal range may be used to confirm a postmenopausal state in women not using hormonal contraception or hormonal replacement therapy (HRT). However, in the absence of 12 months of amenorrhea, confirmation with more than 1 FSH measurement is required.

- Females on HRT and whose menopausal status is in doubt will be required to use 1 of the non-estrogen hormonal highly effective contraception methods if they wish to continue their HRT during the study. Otherwise, they must discontinue HRT to allow confirmation of postmenopausal status before study enrollment.
- Females of non-childbearing potential (premenarchal, documented hysterectomy, documented bilateral salpingectomy, documented bilateral oophorectomy) are not required to use contraception.
  - If the childbearing potential changes after start of the study (e.g. a premenarchal female participant experiences menarche) or the risk of pregnancy changes (e.g. a female participant who is not heterosexually active becomes active), the participant must discuss this with the investigator, who should determine if a female participant must begin a highly effective method of contraception (e.g. LARC) or a male participant must use a condom. If reproductive status is questionable, additional evaluation should be considered.
- For females with permanent infertility due to an alternate medical cause other than the above, (e.g. mullerian agenesis or androgen insensitivity), investigator discretion should be applied to determining study entry.

## Informed Consent

9. Participant and/or parent(s)/legal guardian is capable of giving signed informed consent (and informed assent, as required) as described in [Section 11.1.3](#) of the protocol which includes compliance with the requirements and restrictions listed in the ICF and in the protocol.

## Other

10. For adolescent participants ( $\geq 12$  to  $< 18$  years), a legal guardian must be available to help the study site personnel ensure follow-up; accompany the participant to the study site on each assessment day according to the SoA (e.g. able to comply with scheduled visits, treatment plan, laboratory tests and other study procedures); consistently and consecutively be available to provide information on the participant using the PROs during the scheduled study visits; accurately and reliably dispense study intervention as directed.
11. For adolescent participants, a legal guardian must be able to accurately maintain the child's take-home record, including items of general health.

## 5.2 Exclusion Criteria

Participants are excluded from the study if any of the following criteria apply:

### Medical Conditions

1. Any other inherited or acquired bleeding disorder in addition to hemophilia A. Note: von Willebrand disease should be diagnosed per local clinical practice. Participants with a diagnosis of von Willebrand disease in medical records or diagnosed at the time of screening will be excluded.

2. Platelet count < 100,000/mm^3.
3. Evidence of inhibitor to FVIII ( $\geq 0.6$  BU/mL) within the last 1 year (refer to Inclusion Criterion #5).

### Prior/Concurrent Clinical Study Experience

4. The participant is currently participating in another investigational drug study or has participated in a clinical study involving an investigational drug or device within 30 days of signing informed consent.

### Other Exclusions

5. The participant has a planned major surgery.

Note: Major surgery is defined as any surgical or invasive procedure (elective or emergent) in which the overall bleeding risk may be excessive, would require a general anesthetic in an individual without a bleeding disorder, penetrates or exposes a major body cavity, could result in substantial impairment of physical or physiological functions, or requires special anatomic knowledge or manipulative skill (e.g. tonsillectomy, laparotomy, thoracotomy, joint replacement).

6. Documentation for any of the following risk score parameters is missing/unknown: ABR, pre-study treatment frequency (refer to Inclusion Criterion #4 and [Section 9.4.2](#)), number of target joints affected, and vWF levels.
7. Known hypersensitivity to the drug substance, excipients, or mouse or hamster protein.
8. Any other significant medical condition that the investigator feels would be a risk to the participant or would impede the study.
9. Close affiliation with the investigational site (e.g. a close relative of the investigator) or dependent person (e.g. employee or student of the investigational site).
10. Otherwise vulnerable participants (e.g. participants who are in custody by order of an authority).
11. Judgment by the investigator that the participant should not participate in the study if the participant is unlikely to comply with study procedures (i.e. eDiary completion), restrictions, and requirements.

